Dental implant placement is a highly technique-sensitive procedure. Proper wound closure and stabilization of wound margins in a desired position are critical events that influence the success of the outcomes, particularly in more demanding surgeries such as esthetic and reconstructive surgery.

Wound healing primarily depends on early formation of the blood clot and the establishment of an attachment of the clot that is resistant to mechanical forces acting on the flap and opposing surfaces participating in the wound closure. Suture is the major area of concern in situations where mechanical stability of the flap is required. Ideally, surgical suture should hold edges in apposition until the wound has healed. Various types of sutures have been proposed to stabilize and secure the surgical flap to promote the optimal healing.

For a wound that is deeper in nature, a mattress stitch can be placed, providing better strength. The deeper penetration into the soft tissue layers minimizes tension and allowing for better closure at the wound edges. Mattress sutures can be applied as vertical or horizontal subtypes. According to a previous studies, mean maximum pulling force in a standardized model was 5.69 N (SD, 0.88), 7.25 N (SD, 1.33) and 8.11 N (SD, 1.00) for single interrupted suture, vertical and horizontal mattress suture, respectively. In addition, the blood supply after implant surgery mainly comes from the apex aspect due to the disruption of periosteal blood supply. Thus, the amount and direction of tension of the different subtypes of mattress sutures can have a significant impact on the blood supply after implant surgery.

So far, various studies have compared the effect of horizontal mattress suture (HMS) with vertical mattress suture (VMS) on wound healing in different wound. A 1-year clinical study compared the early healing following HMS with VMS after pancreaticogastrostomy. The result showed that HMS was superior to VMS for preventing early postoperative complications and did not affect pancreatic function. Another study evaluated the medical stitch in trans-osseous-equivalent rotator cuff repair. The results showed that VMS failed at higher loads compared with HMS (568.9 ± 140.3 vs 451.1 ± 174.3 N; $P = 0.025$).

Laser Doppler flowmetry (LDF) is used to measure the tissue blood perfusion noninvasively and has been widely used in the field of plastic surgery. It can detect circulatory disturbances at early stages and predict surgical complications.

However, limited studies have evaluated the effect of the subtype of mattress sutures on the early wound healing and microcirculation changes of peri-implant soft tissues following implant

surgery using LDF. Therefore, it is important to understand the effect of different suture techniques on early wound healing following implant surgery.

3. Study Objectives

The overall aim of this study is to compare the microcirculation changes of peri-implant soft tissues following open-flap implant surgery using different suture techniques. The study also aims to monitor healing dynamics by means of observing volumetric alterations of the peri-implant soft tissues following implant placement.

3.1 Primary Objective

To compare the peri-implant blood perfusion volume responses during healing with horizontal mattress suture and vertical mattress sutures following open-flap implant surgery.

3.2 Secondary Objective

To compare the peri-implant blood oxygen saturation, blood flow velocity and haemoglobin count during healing with horizontal mattress suture and vertical mattress sutures following open-flap implant surgery.

3.3 Additional Objective

To compare three-dimensional soft-tissue volumetric changes, wound healing score and patient-related outcomes (visual analogue scale) during healing with horizontal mattress suture and vertical mattress sutures following open-flap implant surgery.

4. Study Hypothesis

The effect of the different pressure directions of horizontal and vertical mattress sutures on the soft tissue blood supply can be detected by laser Doppler flowmetry.

5. Study Methods

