5.2 Sample Size

Null hypothesis is that no significant difference of blood perfusion volume change (PU) can be found at each time points between two groups. Alternative hypothesis is Significant difference of blood perfusion volume change (PU) can be found at least one time point between two groups.

Because actual difference of primary outcome between two groups may vary. An adaptive design is adopted to adjust planned sample size, type of comparison according to actual statistics calculated from 20 subjects. If the revised sample size is within the planned sample size then the planned sample size is not to be adjusted. If the revised sample size is larger than planned sample size then the revised sample size will be considered. The study population, intervention and primary outcome will stay the same throughout this study.

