7.2 Handing of study interventions

Allocation will be concealed to the surgeon until completion of all surgical steps except for suturing. Thereafter, vertical mattress sutures (test group) or horizontal mattress sutures (control group) will be performed according to the group allocation to achieve wound closure after opening the envelope.

(1) Control group

In the control group, the participants will receive the following sutures to achieve wound closure:

- One mesial single interrupted suture (1 mm from the mesial teeth, 2-3mm from needle-in points to the incision)
- One distal single interrupted suture (1mm from the distal teeth, 2-3mm from needle-in points to the incision)
- One horizontal mattress suture (5-6mm from needle-in points to the incision, 3-4mm from needle-in to needle-out points)

(2) Test group

In the test group, the participants will receive the following sutures to achieve wound closure:

- One mesial single interrupted suture (1mm from the mesial teeth, 2-3mm from needle-in points to the incision)
- One distal single interrupted suture (1mm from the distal teeth, 2-3mm from needle-in points to the incision)
- One mesial and one distal vertical mattress sutures (5-6mm from needle-in points to the incision which are in keratinized tissues, 2-3mm from needle-out points to the incision, 3-4 mm from mesial and distal sutures)

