10.1 Quality Control and Assurance

10.1.1 Training and Calibration

All investigators involved in this study will be trained appropriately for the standard operating procedures including the implant surgery and measurements

- The examiner will be trained and calibrated with the LEA measurements and intra-oral scanning before the start of the study.
- The therapist, who will deliver the implant surgery, will be an experienced specialist in implant dentistry fulfilling the Shanghai requirements.
- The investigator who performs interventions for the test/control groups will be trained in a standardized session including the spacing of the mattress sutures and tension of the knotting.

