11.2 Statistical analysis plan

- (1) Descriptive statistics will be run to describe the demographic, clinical and biological characteristics of the study population. Means with standard deviations (SD) or medians with interquartile range (IQR) will be used to describe continuous variables. Frequencies will be used to describe categorical variables.
- (2) The normality of clinical and biological parameters at baseline and each re-evaluation visit will be tested for normality using the Kolmogorov-Smirnov test. The homogeneity of the clinical and biological parameters at baseline and each re-evaluation visit will be tested using Levene's test.
- (3) The differences over time within groups for data will be analyzed with the non-parametric Wilcoxon's Signed Ranks tests or Paired t-tests according to the data normality and homogeneity.
- (4) The comparison of parameters between the control and the test group at baseline and each re-evaluation visit will be performed with the Mann-Whitney U test or Student t test according to the data normality and homogeneity, respectively.

12. Ethics Requirements and Informed Consent

The Investigators will ensure that this study is conducted in full conformity with the current revision of the Declaration of Helsinki (last amended October 2013). The Investigators will ensure that this study is conducted in full conformity with relevant regulations and with the ICH Guidelines for Good Clinical Practice E6 (R1) July 1996. The protocol, informed consent form and participant information sheet will be submitted to an appropriate Research Ethics Committee (REC) for written approval. A signed consent form will be obtained from each participant. The consent form will describe the purpose of the study, the procedures to be followed, and the risks and benefits of participation. A copy will be given to each participant and this fact will be documented in the participant's record. The trial staff will ensure that the participants' anonymity is maintained.

13. References

Chaudhary Ehtsham Azmat , Martha Council. Wound Closure Techniques. StatPearls [Internet]. Treasure Island (FL): StatPearls Publishing; 2021 Jan. 2021 Jul 27.

Nick Marsidi, Sofieke A M Vermeulen, Tim Horeman, Roel E Genders. Measuring Forces in Suture Techniques for Wound Closure. J Surg Res 2020 Nov;255:135-143. doi: 10.1016

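### Section 4 credits the expected perfusion effect to pressure direction, but direction is completely confounded with the number of mattress sutures (one v two), so a PU difference cannot be attributed to direction

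*Combined protocol and SAP*

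**What the plan says.** Section 4 (Study Hypothesis) is a single sentence. Its substance is this: "effect of the different pressure directions of horizontal and vertical mattress sutures on the soft tissue blood supply can be detected by laser Doppler flowmetry".

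Section 7.2 defines the interventions. Each arm receives one mesial and one distal single interrupted suture, described identically. Beyond these:

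- Control: "One horizontal mattress suture (5-6mm from needle-in points to the incision, 3-4mm from needle-in to needle-out points".
- Test: "One mesial and one distal vertical mattress sutures (5-6mm from needle-in points to the incision which are in keratinized tissues", with the further specification "2-3mm from needle-out points to the incision, 3-4 mm from mesial and distal sutures".

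The Research Background (Section 2) gives a broader mechanism than Section 4. It says that "the amount and direction of tension of the different subtypes of mattress sutures can have a significant impact on the blood supply".

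The objectives in Section 3 compare the two suture techniques and do not mention direction. Section 5.2 frames the null hypothesis as a comparison of groups: "no significant difference of blood perfusion volume change (PU) can be found at each time points between two groups". Section 11.2, item (4), plans the "comparison of parameters between the control and the test group at baseline and each re-evaluation visit". Section 5.3 describes two arms randomised 1:1.

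**The concern.** A hypothesis that names direction as the cause needs a contrast in which direction differs and the other features that could affect perfusion do not, or in which those features vary separately from direction. The two arms here differ in direction and also in how many mattress sutures are placed. An extra suture is not inherent in the distinction between horizontal and vertical. It could plausibly alter the total tension on the flap, and the background itself treats the amount of tension as relevant to blood supply.

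What is at stake is interpretation. If a PU difference is found and read through Section 4, the natural conclusion is that pressure direction affects perfusion. The same data would be equally consistent with an effect of the second mattress suture, or with any mixture of the two.

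**Working it through.** **Plan's own figure.** No figure in the plan bears on this point. The total of 20 subjects comes without an effect size, SD or power, so it cannot be reproduced, and nothing below depends on it.

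**Inputs (Section 7.2).**

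| | Control | Test |
|---|---|---|
| Single interrupted sutures | 1 + 1 = 2 | 1 + 1 = 2 |
| Mattress sutures | 1 horizontal | 1 + 1 = 2 vertical |
| Total sutures | 2 + 1 = 3 | 2 + 2 = 4 |

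**Step 1: relation between direction and number.** Let d = 0 for horizontal and d = 1 for vertical, and let m be the number of mattress sutures. Control patients have (d, m) = (0, 1) and test patients (1, 2). So m = 1 + d for every patient, and the correlation of d with m is 1.

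**Step 2: what can be estimated.** Write the mean PU change at a given time point as

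E(Y) = a + b·d + c·m,

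where b is the effect of direction and c the effect of one additional mattress suture. Substituting m = 1 + d:

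E(Y) = (a + c) + (b + c)·d.

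The design matrix with columns for intercept, d and m has rank 2, not 3. The difference between arms estimates b + c. It does not estimate b.

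**Step 3: illustration.** Let D be the observed difference between arms. Then b = D with c = 0, b = 0 with c = D, and b = −0.5D with c = 1.5D all fit equally well. In a numerical check with 10 patients per arm, assigning 0%, 50%, 100%, −50% and 150% of the difference to direction gave the same residual sum of squares every time. Even the sign of b is not identified.

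**Step 4: does anything else in the plan separate them?**

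- *Sample size revision (Section 5.2).* The intervention is to stay the same throughout, so every added patient again satisfies m = 1 + d. The rank remains 2 at any sample size.
- *Analysis (Section 11.2).* The t test or Mann-Whitney U test compares whole arms at each visit, and so addresses b + c.
- *Training (Section 10.1.1).* The session for the investigator who performs the interventions, "including the spacing of the mattress sutures and tension of the knotting", may make each suture more uniform. It leaves the count at one v two.
- *Measured suture tension (Section 7.3.3, item (5)).* This is recorded after randomisation, immediately after suturing, while the number of sutures is constant within each arm. Adjusting for it would not isolate direction.

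**The case against.** The strongest reply is that this is one loosely worded sentence. Section 4 can be read as a statement that laser Doppler flowmetry can detect a difference, with direction as shorthand for the two techniques. The objectives, the primary outcome, the hypotheses in Section 5.2 and the analysis are already plain comparisons of groups. No other passage commits the investigators to a claim about direction. All of that stands, and it is why the point is minor. Even so, the sentence is the whole of the section headed Study Hypothesis, and its literal words name direction as the cause.

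A reader might also argue that two vertical sutures are needed for closure comparable with one horizontal suture. The documents give no such rationale. If it were true, it would justify comparing schemes; it would not isolate direction.

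Three stronger readings are tempting but not supported:

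- *Bite geometry as a second, separate confounder.* The needle-in distance is 5-6 mm from the incision in both arms. The near bite at 2-3 mm in the test arm is partly what makes a mattress suture vertical, so some of that difference belongs to the direction contrast itself. Nor is it established that equalising the number of sutures would still leave direction unidentifiable.
- *Position as a confounder.* Section 7.2 does not state the mesio-distal position of the horizontal suture. That is a gap in specification, not evidence that position differs in a way that matters.
- *An invalid trial, or sections that contradict each other.* Confounding of components within the interventions does not bias the comparison between arms. Section 4 claims more than the arms defined in Section 7.2 can show, but the two do not state conflicting facts.

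**Conclusion.** The point holds as a limit on interpretation. Direction is completely confounded with the number of mattress sutures (one v two; three v four sutures in total), so the hypothesis as worded in Section 4 cannot be answered by this design. A PU difference would support a statement about the two closure schemes and nothing narrower.

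The size of any effect of the extra suture on PU cannot be computed from the documents, and they do not indicate which explanation is more plausible. The conclusion rests only on the suture counts in Section 7.2 and on there being two arms with no variation in number within direction.

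This point leaves the randomised comparison, its estimates and its error rates as they are. It says nothing either way about other aspects of the design. Severity: minor.

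**What to change.** Restate the Section 4 hypothesis to agree with Sections 3 and 5.2. For example: PU change differs at one or more time points between closure with two interrupted sutures plus one horizontal mattress suture and closure with two interrupted sutures plus two vertical mattress sutures, as specified in Section 7.2.

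In the report, limit the conclusion to these two schemes, and add one sentence saying that direction and number of mattress sutures cannot be separated, so no difference is attributed to pressure direction.

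No change to surgical technique, sample size or tests is proposed. The cost is one sentence in the protocol and one in the report. The downside is a narrower claim with no statement about mechanism.

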5.1 Overall Design of the Study

This will be a parallel group, single - centred, open-label, adaptive-design clinical trial with balanced randomization.

5.2 Sample Size

Null hypothesis is that no significant difference of blood perfusion volume change (PU) can be found at each time points between two groups. Alternative hypothesis is Significant difference of blood perfusion volume change (PU) can be found at least one time point between two groups.

Because actual difference of primary outcome between two groups may vary. An adaptive design is adopted to adjust planned sample size, type of comparison according to actual statistics calculated from 20 subjects. If the revised sample size is within the planned sample size then the planned sample size is not to be adjusted. If the revised sample size is larger than planned sample size then the revised sample size will be considered. The study population, intervention and primary outcome will stay the same throughout this study.

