7.1.2 Surgical procedures

One experienced specialist in Implant Dentistry will perform the implant surgeries for all patients. Surgery will be standardized, and the same procedures/materials will be employed to ensure consistency.

- Local anesthesia will be performed by infiltration at the buccal vestibular sulcus and the palatal side of the alveolar ridge.
- Following anesthesia, a mid-crestal ridge incision will be started and continue with sulcular incisions around both adjacent teeth to the implant bed using blades #.11 or No.12.
- A full-thickness mucoperiosteal flap will be raised and soft tissue remnants will be removed to fully expose the alveolar ridge.
- A standardized dental implant (Nobel Active) will be placed according to the manufacturer's instructions. Cover screws will be used.
- Different suture techniques will be used according to the group allocation to achieve wound closure after opening the envelope.
- The sutures will be removed after 7 days.

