The LDF measurements at the test and control group will be performed on the day of the surgery before the injection of the local anaesthesia (baseline), 1min following local anaesthesia induction, immediately following completion of the surgical procedure, post-operative hours 1,2,6 and on post- operative days 1, 3, 7, 14, 30.

(5) Suture tension (Flap Tension Meter)

Immediately after suture, the tension exerted on the flap margins with the respective sutures was measured using a highly sensitive electronic tension/pressure device (Flap Tension Meters, Imedico GmbH, Zurich ZH, Switzerland). Tension was read to an accuracy of 0.001N (0.1 g).

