7.3.4 Follow-up Visits and evaluation

Follow-up assessment will be performed by the same trained clinician, blind with respect to the group assignment, additional assessments including:

(1) Soft tissue thickness

The thickness of the soft tissue will be performed with calipers 2 mm from incision margin in both buccal and palatal side.

(2) Clinical wound healing assessment

EHI index will be used for clinical wound healing assessment: a) complete flap closure – no fibrin line in the interproximal area; b) complete flap closure – fine fibrin line in the interproximal area; c) complete flap closure – fibrin clot in the interproximal area; d) incomplete flap closure – partial necrosis of the interproximal tissue; e) incomplete flap closure – complete necrosis of the interproximal tissue.

(3) Patient-reported outcomes

Visual analogue scale (0-10) will be used to evaluate the post-operative pain.

Immediate after anesthesia – T1

- LEA measurement
- Soft tissue thickness (after flap elevation)

Immediate after suture – T2

- LEA measurement
- Intra-oral scanning
- Suture tension
- PROMs

1 hour after surgery – T3

- LEA measurement
- Intra-oral scanning

2 hours after surgery – T4

- LEA measurement
- Intra-oral scanning

6 hours after surgery – T5

- LEA measurement
- Intra-oral scanning
- PROMs

24 hours after surgery – T6

- LEA measurement
- Intra-oral scanning
- Clinical wound healing assessment
- PROMs

72 hours after surgery – T7

- LEA measurement

- Intra-oral scanning
- Clinical wound healing assessment
- PROMs

7 days after surgery – T8

- LEA measurement
- Intra-oral scanning
- Suture removal
- Clinical wound healing assessment
- PROMs

14 days after surgery – T9

- LEA measurement
- Intra-oral scanning
- Clinical wound healing assessment

30 days after surgery – T10

- LEA measurement
- Intra-oral scanning
- Clinical wound healing assessment

8. Outcomes and evaluations

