8.1 Outcomes

8.1.1 Primary outcomes

- Blood perfusion volume (PU) change during the observation period

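### The primary hypothesis names neither its time points nor the reference for change, so a reading taken before any suture is placed (T1) can satisfy it; T1's own effect is small

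*Combined protocol and SAP*

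**What the plan says.** **Hypothesis and outcome.** Section 5.2 sets the alternative as "Significant difference of blood perfusion volume change (PU) can be found at least one time point between two groups". Section 8.1.1 defines the primary outcome as "Blood perfusion volume (PU) change during the observation period". Neither lists time points or names a reference reading.

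**Tests.** Section 11.2(4) compares parameters, not changes, between arms at baseline and at each re-evaluation visit, by Student t or Mann-Whitney test. Section 11.1 sets 0.01 for every test.

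**Schedule.** Section 7.3.3 places the first two laser Doppler readings "before the injection of the local anaesthesia (baseline), 1min following local anaesthesia induction". Section 7.3.4, on follow-up visits, opens its list with "Immediate after anesthesia – T1", including a perfusion reading. The first reading after suturing is T2 and the last is T10 (day 30).

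**When the arms diverge.** Section 7.1.2 says "Different suture techniques will be used according to the group allocation to achieve wound closure after opening the envelope", and section 7.2 says "Allocation will be concealed to the surgeon until completion of all surgical steps except for suturing". Up to suturing, both arms receive the same procedure.

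**Stated intent.** Section 3.1 gives the primary objective as "To compare the peri-implant blood perfusion volume responses during healing with horizontal mattress suture and vertical mattress sutures following open-flap implant surgery". The hypothesis in section 4 concerns "The effect of the different pressure directions of horizontal and vertical mattress sutures on the soft tissue blood supply".

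**The concern.** The claim under test is about sutures, but the rule for declaring success is not limited to readings that a suture could have influenced. T1 is scheduled, measured with the primary instrument and grouped with the follow-up evaluations. If the arms differed there at p < 0.01 and nowhere else, section 5.2 taken literally would count the primary alternative as met. That difference could not be a suture effect. It would reflect chance, or a failure of concealment or measurement.

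The second gap is the reference for change. Section 7.3.3 calls the pre-anaesthesia reading baseline, but no section says that PU change is the difference from it, and 11.2(4) can be read as comparing raw values. Section 5.2 also lets the type of comparison be adjusted from the statistics of the 20 subjects, without saying what that covers. An analysis choice that is still open once data are available can raise the false-positive rate.

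**Working it through.** **Inputs from the documents.** 20 subjects at 1:1, so 10 per arm (sections 1 and 5.3); 0.01 per test (11.1); readings T0 to T10 (7.3.3, 7.3.4). Of these, T2–T10 are the 9 post-suture readings, T1–T10 the 10 readings after baseline, and T0–T10 all 11. The sample size of 20 cannot be reproduced, because no effect size, SD or power is given; this point does not depend on it.

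**Assumptions.** Two-sided tests; one PU value per patient per time point; normal data; correlation over time either exchangeable (0.3, 0.5, 0.7) or first-order autoregressive (0.5, 0.8). The documents give no PU correlations.

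**Step 1: ceiling with independent tests,** 1 − 0.99^k.
- T2–T10: 1 − 0.99^9 = 8.65%
- T1–T10: 1 − 0.99^10 = 9.56%
- T1 therefore adds at most 9.56 − 8.65 = 0.91 points.

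**Step 2: null simulation** (10 per arm, 60,000 trials per correlation structure).

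| Analysis | Result over the five structures |
|---|---|
| Change from T0, t-tests, any of T2–T10 | 5.3–7.1% |
| Change from T0, t-tests, any of T1–T10 | 6.1–7.7% |
| Change from T0, t-tests, T1 significant and none of T2–T10 | 0.55–0.73% |
| The same T1-only event, exact Mann-Whitney (attained size 0.0089) | 0.52–0.69% |
| Raw values (t or Mann-Whitney), T1 significant and none of T2–T10 | 0.36–0.86% |

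**Step 3: open reference.** Under the same five structures, fixing either change from T0 or raw values in advance gives about 5–8% for any of T2–T10. Counting a success on whichever of the two is significant gives about 10–14%.

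**Step 4: ANCOVA on T0 against change scores.** Let ρ be the correlation of T0 with the later reading and k the later SD divided by the T0 SD. In units of the T0 variance, a change score has variance k² + 1 − 2ρk. ANCOVA has k²(1 − ρ²), times 1 + 1/(20 − 4) = 17/16 for chance baseline imbalance.
- k = 1: the ratio is (1 + ρ)/2 × 17/16 = 0.691, 0.797 and 0.903 at ρ = 0.3, 0.5 and 0.7, a saving of about 31%, 20% and 10%.
- k = 1.5: 0.93, 1.03 (1.025 before rounding) and 1.06. For example, at ρ = 0.7, 2.25 × 0.51 × 1.0625 / (3.25 − 2.1) = 1.219/1.15 = 1.06.
- k = 2: 1.02, 1.06 and 0.99.
- The loss is bounded. The change-score variance minus k²(1 − ρ²) equals (1 − ρk)², which is never negative, so the ratio cannot exceed 17/16 = 1.0625, a loss of about 6%. The lost degree of freedom (17 instead of 18) multiplies by (2.898/2.878)² = 1.014, giving 1.0625 × 1.014 = 1.077, about 8%.

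**Step 5: what remains after the fix.** With ANCOVA, the chance of at least one false positive across T2–T10 is 6.5–8.2%, against 6.1–7.7% for T1–T10 change scores in step 2. The overall error does not fall.

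**The case against.** The best defence is that the protocol, read as a whole, already excludes T1. Section 3.1 speaks of healing after surgery, section 4 of an effect of the sutures, and a reading one minute after anaesthesia is hardly a re-evaluation visit. Likewise T0 is labelled baseline, so change from T0 is the ordinary reading. This stands as evidence of intent, and it makes the gap a missing link between sections rather than a missing schedule. It does not close the gap. Re-evaluation visit is not defined, 7.3.4 groups T1 with follow-up, and 11.2(4) itself tests the arms at another pre-suture reading, baseline.

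A reader might infer more than the documents support:

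- **That T1 seriously inflates the primary error rate.** Its share is under 1 point when there is one value per patient. Larger figures need separate testing of the six measurement sites, a rule the plan does not state.
- **That a T0 difference could also meet the hypothesis.** Only if raw values are compared; change from T0 is zero at T0.
- **That a T1 difference can only be chance.** Concealment is stated for the surgeon. Section 5.4 says the examiner cannot be blinded, while 7.1.3, 7.3.3 and 7.3.4 describe a blinded assessor. A T1 difference could therefore also signal a procedural failure, and T1 is worth keeping as a check.
- **That ANCOVA always saves variance at moderate correlation.** Step 4 shows that this depends on the ratio of SDs, which the documents do not give.

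**Conclusion.** The point holds as a minor defect of wording. As written, the primary alternative can be met by a reading that precedes the intervention. T1 alone does this in about 0.5–0.7% of null trials with change from T0 and 0.4–0.9% with raw values, given one value per patient, 10 per arm, two-sided 0.01 and the assumed correlations.

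Small describes T1 only. The unstated reference could raise the T2–T10 false-positive rate to about 10–14% if change or raw values were picked after seeing the data. Nothing in the documents shows that such a choice is intended; they simply do not rule it out.

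**What to change.** **Wording, before any analysis.** In 5.2, 8.1.1 and 11.2(4), state that PU change is measured from T0, name T2–T10 as the primary family, and report T0 and T1 descriptively by arm, without significance tests, as a check on balance, concealment and measurement. This needs no new data or visits.

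**Separately, as a gain in precision unrelated to T1.** Replace the unadjusted between-arm tests at T2–T10 with ANCOVA on the T0 reading already collected, rank-based if the data are not normal. The cost is one degree of freedom and the 17/16 variance factor at 10 per arm. Against change scores, the saving is about 31%, 20% and 10% at correlations of 0.3, 0.5 and 0.7 only if T0 and later SDs are equal. It is larger if the later SD is smaller. It can vanish, or become a loss of up to about 6% (8% with the lost degree of freedom), if the later SD is 1.5–2 times the T0 SD.

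**Still open.** Neither change controls the error of testing nine time points. Section 11.2 needs its own multiplicity rule for T2–T10.
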